Appendix 1. Overview of MSM web platforms and screen shots.

We will partner with the largest CBO, Danlan. This CBO provides sexual health services such as HIV and syphilis rapid testing and counseling, as well as linkage to care (accompaniment to clinical services for infected individuals). To engage MSM in health-seeking behaviors, the CBO also maintains a web platform where MSM can participate in sexual health forums, find out about LGBT-related events, and catch up on news stories concerning LGBT communities. These web platforms also serve as portals to other websites of interest to MSM, such as social networking sites WeiBo and BF99, movie databases, and gay mobile app sites like Blued and Jack'd.

Figure 1. Screenshots of the MSM web portal in Beijing, Danlan Gongyi.

| Appendix 2. Sec | ondary outcomes | measured as | part of this RCT. |
|------------------|-----------------|-------------|-------------------|
| rippondin 2. Dec | ondary outcomes | mousureaus | pure or end recre |

| Secondary Outcome | Definition | | |
|-----------------------|--|--|--|
| Incremental cost | Incremental cost, defined as the cost associated with respective | | |
| | video interventions (development, start-up, implementation, | | |
| | condom use, intervention – see Table 1 below for details) per | | |
| | individual who reported no sex or sex with a condom during the | | |
| | follow-up period. | | |
| Female condomless | Frequency of men, defined as number of men who reported | | |
| sex | condomless vaginal or anal sex with a woman divided by the | | |
| | total number of men who viewed the video in that arm. | | |
| Male condomless sex | Frequency of men, defined as number of men who reported | | |
| | condomless anal sex with a man divided by the total number of | | |
| | men who viewed the video in that arm | | |
| Post-video condomless | Frequency of men, defined as number of men who reported | | |
| sex | condomless vaginal or anal sex with any partner immediately | | |
| | following the video intervention divided by the total number of | | |
| | men who viewed the video in that arm | | |
| Frequency of sex acts | Frequency of men, defined as the number of men who had | | |
| | decreased total number of sex acts in the three weeks following | | |
| | the intervention compared to the three weeks immediately | | |
| | preceding the intervention in that arm | | |
| Condom use social | Frequency of men, defined as number of men who report higher | | |
| norms | levels of social norms when comparing their pre-intervention | | |
| | and post-intervention condom use norms* | | |
| Condom self-efficacy | Frequency of men, defined as number of men who had an | | |
| | increase in self-efficacy when comparing their pre-intervention | | |
| | and post-intervention self-efficacy** | | |
| Condom negotiation | Frequency of men, defined as the number of men who attempted | | |
| | to convince an unwilling partner to use a condom immediately | | |
| | following the video intervention divided by the total number of | | |
| | men who viewed the video in that arm | | |
| HIV testing | Frequency of men, defined as the number of men who reported | | |
| | being tested for HIV during the interval between watching the | | |
| | video and following up compared to the number of men who | | |
| | followed up | | |
| STI testing | Frequency of men, defined as the number of men who reported | | |
| | being tested for STIs (excluding HIV) during the interval | | |
| | between watching the video and following up compared to the | | |
| | number of men who followed up | | |

*Condom use social norms will be measured using six survey items that are each on a five point Likert scale. Increased condom use social norms will be defined as having an increase from baseline in any two of these six survey items and dichotomized accordingly. The condom use social norm outcome will be assessed in the entire group as well as the subgroup of men who were referred by their friends.

**Self-efficacy will be measured using seven survey items that are each on a five point Likert scale. Increased self-efficacy will be defined as having an increase from baseline in any two of these seven survey items and dichotomized accordingly. The self-efficacy outcome will be assessed in the entire group as well as the subgroup of men who were referred by their friends.

| | Financial costs | Economic costs |
|--|--|--|
| Phase | | |
| Contest development | Inputs to be captured, can all directly be found in the project financial accounts, main challenge is to allocate across components and to allocate SESH overhead costs | Extra inputs not already captured by financial costs |
| Video contest (including production) | Money paid for planning and implementation | For social marketing arm: Personnel of CBOs/CDC(director of movie, actors, film editors) Rental of professional video equipment (if applicable) Building cost (office renting) for CBOs/CDC* Equipment and software cost (if applicable) * For crowdsourced arm: Personnel of SESH (although all volunteer) Judging opportunity cost (volunteer) Steering Committee planning meeting (three one-hour meetings) Building cost (office renting)* In-person promotion costs |

Table 1. Incremental costs associated with social marketing and crowdsourced arms.

| Survey start up | Money paid to launch the survey (start-up); | • | SESH personnel costs, to design and maintain the program Equipment cost of SESH (computer and other items)* Software (Proof Pilot, Qualtrics)* |
|--|---|---|--|
| Survey implementation and intervention | Money paid to the participants (implementation); Money paid for the software used for follow up (implementation): | • | SESH personnel costs |
| Testing | (r), | • | Cost for condoms (from CDC) |

*The cost will be annualized and we will calculate a proportion of the cost to account for them only being used the study time frame. The key idea is that some of these phases are like capital goods, where they only need to be done once but have benefits for longer (thus requiring annualization of costs), while the implementation phase has a life only as long as the survey is running.

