Statistical Analysis: The primary outcome will be condomless vaginal or anal sex (with any sex partner) among MSM and transgender individuals following the assigned video intervention. Participants will be asked about using condoms all the time or not using condoms all the time since watching the video (individuals who have not had sex in the interval will be classified as no condomless sex). Condomless vaginal or anal sex includes condomless sex of any frequency (e.g., always condomless sex, occasional condomless sex, etc.). We will examine the non-inferiority hypothesis comparing the two interventions, as well as the superiority hypothesis. The difference in proportions having condomless sex (crowdsourced – social marketing) will be estimated, with a corresponding two-sided 95% Wald confidence interval. The crowdsourced intervention will be declared non-inferior to social marketing if the upper confidence limit is below 10%. If the upper confidence bound is below 0%, then the crowdsourced intervention will be declared superior to social marketing.

Our secondary outcomes are condom use self-efficacy, cost, and related behavioral outcomes. The objective of the cost analysis will be to estimate the total and incremental unit cost in using

video interventions to promote condom use. In this step, we will further collect cost related data from all the organizations involved in making condom use promotion videos. Detailed information that we will collect from these organizations is listed in Appendix 2. One of our secondary analyses will focus on those individuals who reported sex following the video intervention (excluding those who did not have sex in the interval between the video and the survey).

Missing Data Plan: Missing data in the primary outcome that accounts for <11% of participants will not be imputed and the complete-case approach will be used. However, in cases where missing data for the primary outcome is 11 to <20% of the total outcome, a sensitivity analysis using multiple imputation based on the PROC MI procedure in SAS (Cary, NC) will be used. If missing data accounts for \geq 20% of participants then we will use multiple imputation in the primary analysis.

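### Appendix 2 divides four secondary outcomes by everyone who viewed the video, so non-responders count as non-events; rates are diluted and, if loss differs by arm, comparisons are biased

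*Protocol*

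**What the plan says.** Protocol, Appendix 2, gives a formula for each of four outcomes: female condomless sex, male condomless sex, post-video condomless sex and condom negotiation. The numerator is the men who reported the behaviour (for negotiation, the men who attempted it). The denominator is the "total number of men who viewed the video in that arm".

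The post-video item counts men who reported "condomless vaginal or anal sex with any partner immediately" after the video. Section 5, Statistical Analysis, defines the main endpoint in nearly the same terms: "The primary outcome will be condomless vaginal or anal sex (with any sex partner) among MSM and transgender individuals following the assigned video intervention".

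Other parts of the protocol handle men without follow-up data differently:

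- **Statistical Analysis (section 5)** gives one group the favourable classification by rule: "individuals who have not had sex in the interval will be classified as no condomless sex". It does not extend this to men who never reply.
- **Missing Data Plan (section 5)** says: "Missing data in the primary outcome that accounts for <11% of participants will not be imputed and the complete-case approach will be used". From 11% to below 20% missing, multiple imputation is added as a sensitivity analysis. From 20% it becomes the primary analysis.
- **Sample size calculation (section 5)** treats lost participants as not evaluable: 526 evaluable out of 585 per arm.
- **HIV and STI testing (Appendix 2)** use the men who followed up as denominator: "video and following up compared to the number of men who" did so.
- **Incremental cost (Appendix 2)** counts as successes only people who reported abstinence or condom use, so a non-responder is not a success there.

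**The concern.** Behaviour after the video is known only from replies to the follow-up surveys. A man who watched the video and never replied therefore sits in the denominator and cannot enter the numerator. Under these formulas he is recorded as having had no condomless sex and as not having negotiated condom use. Nothing in the protocol justifies either assumption, and no other part of it handles missing follow-up this way.

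Two things are at stake. First, the four rates are understated, and any real difference between arms shrinks towards zero. Second, if the arms lose different proportions, the difference in loss shows up as a difference in behaviour. For condomless sex, an unfavourable event, the arm with more loss looks better. For negotiation, a favourable event, it looks worse.

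The post-video item adds a further problem. If it is the primary outcome under another name, the trial would report one endpoint with two denominators and two different rates.

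**Working it through.** **Inputs.** From section 5, Sample size calculation, its table and table note: event probability 0.50 in each arm, margin 0.10, one-sided α 0.025, power 0.90, loss about 10%, 585 per arm, pilot rate 9/25 = 0.36. Arm-specific loss is not given, so every unequal split below is an assumption.

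**1. The plan's own figure.** n = (1.960 + 1.2816)² × [0.5×0.5 + 0.5×0.5] / 0.10² = 525.37, so 526 evaluable per arm. 526/0.90 = 584.4, so 585 per arm and 1170 in total. The stated figures reproduce. They also show that the sample size excludes lost men from the evaluable number.

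**2. Formula.** Let p be the true rate and L the proportion lost in an arm, with loss unrelated to outcome. The rate among men followed up is p. The rate with the viewer denominator is p × (1 − L). Whatever the loss mechanism, the viewer rate cannot exceed the true rate, because unreported events are dropped; the factor (1 − L) is what needs the assumption.

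**3. Equal loss at the planned 10%.**

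- 0.50 × 0.90 = 0.45.
- 0.36 × 0.90 = 0.324.
- In counts: 526 replies and 263 events give 263/526 = 50.0% among men followed up, but 263/585 = 45.0% among viewers.
- A true 12-point difference (48% against 36%) becomes 0.432 − 0.324 = 0.108, that is 10.8 points.
- A null difference stays at zero.

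**4. Unequal loss, no true difference.** The spurious difference is p × (difference in loss). The arm with more loss has the lower rate.

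| Loss in the two arms (assumed) | p = 0.36 | p = 0.50 |
|---|---|---|
| 10% and 10% | 0 | 0 |
| 12% and 8% | 0.36 × 0.04 = 1.4 points | 0.50 × 0.04 = 2.0 points |
| 15% and 5% | 0.36 × 0.10 = 3.6 points | 0.50 × 0.10 = 5.0 points |

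All three splits average 10%. The sign depends only on which arm loses more. If the crowdsourced arm does, it appears to have less condomless sex; if the social marketing arm does, the reverse. With the followed-up denominator the expected difference is zero in every row.

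For scale, at p = 0.50 with 12% and 8% loss the viewer rates are 0.44 and 0.46. The 95% Wald half-width at 585 per arm is 1.96 × √[(0.44×0.56 + 0.46×0.54)/585] = 5.7 points.

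**5. Negotiation.** The same formula applies, but the event is desirable, so a lower rate counts against the arm with more loss. The documents give no rate for this outcome, so no size is computed.

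**6. Is the post-video item the primary outcome?** Both cover vaginal or anal sex, any partner, after the video. The appendix places the item immediately after the video and gives no window. Section 5 schedules outcome collection at three weeks and three months, with no separate assessment straight after viewing. The note to the sample size table describes the pilot rate as covering the three weeks immediately following the video. The two therefore look like the same endpoint. At 10% loss the Missing Data Plan requires complete-case analysis, which gives 50% in step 3, while Appendix 2 gives 45% from the same replies.

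**The case against.** The strongest reply is that this lies outside the trial's main claim. The non-inferiority rule in section 5 (upper 95% limit below 10%) is stated for the primary outcome, which has its own missing-data plan. None of the four outcomes has a margin, and self-efficacy, the one secondary outcome with a non-inferiority hypothesis, is not defined by viewers. This stands. A reader might infer that dilution and unequal loss make the trial's non-inferiority conclusion too easy to reach; the protocol does not support that, because the primary test is not defined with this denominator.

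A reader might also infer that the bias favours crowdsourcing. It does so only if that arm loses more, and on negotiation it would then count against it. Both arms watch a one-minute video with the same follow-up and incentives, and nothing in the protocol predicts unequal loss. At equal loss a null result stays null.

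Third, the Missing Data Plan is worded for the primary outcome only, and handling for secondary outcomes could be left to a statistical analysis plan. So a direct contradiction can be claimed only for the post-video item, and only if it is the primary outcome, which is likely but not certain. For the other three the fault is an inconsistency of method. It is still not a matter of missing detail: Appendix 2 writes out the formulas, and followed literally they treat non-response as a non-event.

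Finally, conditioning on viewing could be criticised as a post-allocation restriction. The protocol does not say how many randomised men fail to view, or that this differs by arm, so nothing is rested on it here.

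**Conclusion.** The point holds at moderate weight, for secondary outcomes. Four formulas in Appendix 2 count non-responders as non-events, out of line with section 5 and with the testing outcomes in the same appendix. At the planned equal 10% loss, rates are understated by a tenth of their value and any true difference shrinks by a tenth. These sizes rest on loss being unrelated to outcome. Under unequal loss the comparison is biased by the event rate times the difference in loss: 1.4 to 2.0 points of condomless sex for an assumed 12% against 8%, with the direction set by which arm loses more and reversed in meaning for negotiation. The sample size and the primary decision rule are unaffected. The sharpest part is the post-video item: if it is the primary outcome, the protocol gives two incompatible rules for the same endpoint.

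**What to change.** In Appendix 2:

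1. For all four outcomes, replace the viewer denominator with participants randomised to the arm who have an outcome report at that follow-up. Alternatively, use all randomised participants with multiple imputation, following the Missing Data Plan's thresholds, and say that the plan extends to these outcomes.
2. Label post-video condomless sex as the primary outcome and remove it from the secondary list, or state the time window that makes it different.
3. If the viewer denominator is kept, show it only as a sensitivity analysis, labelled as counting non-responders as non-events.

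The cost is a wording change in one appendix. No data collection, sample size or primary analysis changes. Reported rates become somewhat higher: at 10% loss, 50% instead of 45%, or 36% instead of 32.4%.

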Main and Secondary Outcomes: The main outcome of this study will be any condomless anal or vaginal sex with any sex partner at three weeks and three months following the video. Individuals who do not reply to the three week message will receive a second message at four weeks. Secondary outcomes include cost, self-efficacy, and other behavioral variables (Appendix 2).

Eligibility and Recruitment: Participants will be recruited through a banner link on a popular MSM web portal home page and an announcement sent to registered users by email and other social media platforms. Interested participants who click on the link will then be directed to the survey with a description of its contents and an online informed consent form. The survey is voluntary and to be eligible, participants must state that they were born biologically male or are transgender, had anal sex with men at least once during their lifetime, have had condomless anal/vaginal sex in the past three months, and are at least 16 years of age. All participants must provide their cell mobile number. Individuals identified by their cell phone number who enter the study twice and watch different videos will be excluded. No names or addresses will be collected from participants. All individuals who enroll in the study and reply to the text message will receive a 100 RMB (8.50 USD) pre-paid cell phone card for their time at the first FU and a 50 RMB pre-paid card for the second FU.

Measures: Survey items on socio-demographics and sexual behaviors will be collected using standardized survey instruments immediately before video watching, three weeks after video watching, and three months after video watching. Socio-demographic characteristics include participants' age, highest level of education completed, annual income, marital status, sexual orientation, and sexual orientation disclosure. Behavioral variables include number of sex acts in the past three weeks, condomless sex with men, condomless sex with women, condom self-efficacy, and other secondary outcomes specified in Appendix 2.

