Effect modification analyses: Effect modification analyses will be undertaken based on prior exposure to condom promotion video watching to assess whether this exposure differs between the baseline groups. A linear probability model will be used to evaluate effect modification by testing for an interaction between intervention and prior video watching (e.g.,

 $Prob(Condomless Sex = 1 | Arm, AgeGrp) = \alpha + \beta_1 Arm + \beta_2 AgeGrp + \beta_3 Arm * AgeGrp).$ This model can be fit with the GENMOD procedure in SAS using the binomial distribution and identity link. If this model does not converge, then log-binomial regression will be used to estimate relative risks. *Secondary analysis:* We will examine the subset of individuals who reported sex during the follow-up period (3 weeks and 3 months respectively) and use causal inference methods to account for post-randomization selection bias. We will compare the proportion of individuals who have any sex between the two arms to determine if the intervention results in less frequent sex.

Sample size calculation: To calculate sample size we assumed an equal probability of reported condomless sex in the crowdsourced video intervention and social marketing intervention arms. We calculated the sample size for this binary outcome non-inferiority trial using the formula below with a one-sided significance level (α) of 2.5% and power (1- β) of 90%.²¹ Assuming a 50% probability of condomless sex in each arm, a non-inferiority limit of 10%, and loss to follow-up of 10%, a total sample size of 1170 individuals is required (585 in each arm). The sample size calculation was made using the formula:

$$n = f(\alpha, \beta) \frac{[\pi_s (1 - \pi_s) + \pi_e (1 - \pi_e)]}{(\pi_s - \pi_e - d)^2}$$

where π_s and π_e are the true probability of reported condomless sex in the social marketing intervention and crowdsourced video (experimental) intervention groups, respectively, d is the non-inferiority limit, and $f(\alpha, \beta) = [\Phi^{-1}(\alpha) + \Phi^{-1}(\beta)]^2$, where Φ^{-1} represents the cumulative distribution function of the standard normal distribution.

Sample size calculations for 90% power and a one-sided 0.025 significance level

| Probability | Probability | Non- | Probability of | Ν | Total |
|-------------|-------------|------------|-----------------------|---------|----------|
| of primary | of primary | inferiorit | loss to follow- | evaluab | sample |

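### The HIV-testing outcome counts men already diagnosed with HIV, which modestly dilutes the uptake rate and the absolute arm difference; a baseline-defined denominator would remove most of this

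*Protocol*

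**What the plan says.** The HIV-testing row of Appendix 2 takes as numerator the men who reported "being tested for HIV during the interval between watching the" video and follow-up. The denominator is given in the same row, "video and following up compared to the number of men who" followed up, with no restriction by HIV status.

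Section 5, under Eligibility and Recruitment, sets the entry conditions: "participants must state that they were born biologically male or are transgender, had anal sex with men at least once during their lifetime", and further "have had condomless anal/vaginal sex in the past three months, and are at least 16 years of age". A mobile number is also required. The only exclusion stated there concerns duplicate entry: "Individuals identified by their cell phone number who enter the study twice and watch different videos will be excluded". None of these conditions refers to HIV status.

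Under Measures, the same section names examples of what is collected: "Behavioral variables include number of sex acts in the past three weeks, condomless sex with men, condomless sex with women, condom self-efficacy", followed by a reference to the other outcomes in Appendix 2. Prior HIV diagnosis is not among the named items.

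**The concern.** A man diagnosed before the video has no diagnostic test left to take up. Under the written rule he still enters the denominator. If he reports no test, he is scored like an undiagnosed man who chose not to test. If he reports a test done in the course of care, he is scored like an undiagnosed man who took one up. Neither score describes testing uptake.

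Such participants are a realistic prospect on the Protocol's own account. The Background describes high HIV incidence among MSM. Appendix 1 says the partner organisation offers HIV testing and helps infected men reach care, and recruitment runs through an MSM web portal. At stake is whether the reported rate can be read as uptake among men who could test, and how far the absolute arm difference is diluted. Because the Protocol itself fixes this denominator, the point is not simply left to an analysis plan.

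**Working it through.** **The plan's own figure.** The only sample-size figure is for the primary outcome, at a "one-sided significance level (α) of 2.5% and power (1- β) of 90"%. With 0.50 in each arm and a margin of 0.10:

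- n = (1.960 + 1.282)² × (0.25 + 0.25) / 0.10² = 525.4, so 526 evaluable per arm.
- 526 / 0.9 = 584.4, so 585 per arm and 1170 in total.

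This matches the Protocol, and HIV testing plays no part in it. I use 526 below as the number followed up per arm.

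**Inputs that are assumptions.** The Protocol gives neither the diagnosed share nor any testing rate. Let p be the diagnosed share of followed-up men, r the testing rate among undiagnosed men, and t the share of diagnosed men who report a test. For illustration, r is 30% in one arm and 38% in the other.

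**Formula.** Reported rate = (1−p)·r + p·t. Reported difference = (1−p)·(r₂−r₁) + p·(t₂−t₁).

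**Full-dilution case, t = 0 in both arms.** The rates and the difference are multiplied by (1−p). At p = 10%: 0.9 × 30% = 27.0%, 0.9 × 38% = 34.2%, difference 7.2 points instead of 8.0.

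| p | Diagnosed men per arm (526p) | Reported rates | Reported difference | True / reported rate, 1/(1−p) | Power, all followed up | Power, diagnosed excluded |
|---|---|---|---|---|---|---|
| 3% | 16 | 29.1% v 36.9% | 7.8 | 1.031 | 0.766 | 0.772 |
| 5% | 26 | 28.5% v 36.1% | 7.6 | 1.053 | 0.753 | 0.764 |
| 10% | 53 | 27.0% v 34.2% | 7.2 | 1.111 | 0.720 | 0.741 |
| 15% | 79 | 25.5% v 32.3% | 6.8 | 1.176 | 0.684 | 0.717 |

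Power is a normal approximation at two-sided 5%: 526 per arm with the diluted rates, against 526(1−p) per arm with the undiluted rates. The risk ratio is 38/30 = 1.267 in every row, because (1−p) cancels.

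**If some diagnosed men do report a test.** Take t = 30% in both arms and p = 10%. The reported rates are 27.0% + 3.0% = 30.0% and 34.2% + 3.0% = 37.2%. The rates fall less than in the full-dilution case. The difference is still 7.2 points, and the risk ratio becomes 37.2/30.0 = 1.24. So (1−p) is the largest shrinkage of the rate. It is also the largest shrinkage of the difference, unless reported testing among diagnosed men runs against the arm effect.

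**Balance between arms.** Randomisation makes p equal in expectation. At p = 8%, the chance standard deviation of the between-arm difference in p is √(2 × 0.08 × 0.92 / 526) = 1.7 percentage points, with no preferred direction.

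**The case against.** The strongest reply is that testing among everyone who followed up is a coherent population-level rate, keeps all responders and matches the STI-testing row. On that view uptake is understated only if one prefers the rate among undiagnosed men. This is a fair point about the choice of estimand. It does not remove the difficulty that a diagnosed man's record carries no information on uptake, whichever way it is scored.

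Four further limits stand in full.

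- The outcome counts any reported HIV test, not a first or diagnostic one. Scoring every diagnosed man as untested is therefore an assumption, and the table shows the full-dilution case.
- HIV testing has no hypothesis, margin or power claim. The hypotheses in section 4 concern condom use, cost and self-efficacy.
- Both videos promote condom use, and nothing in the Protocol predicts a testing difference. The 30% v 38% is illustrative; if the true difference is near zero, so is its dilution.
- A denominator based on self-reported diagnosis is itself imperfect.

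A reader might also infer that HIV status is not collected at all. The Protocol does not support that. The Measures paragraph gives examples rather than the questionnaire, and prior exposure to condom videos is not named there either, although the effect-modification analysis uses it. Finally, a reader might infer that the dilution helps a non-inferiority claim by making the videos look alike. No such claim is planned on this outcome.

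**Conclusion.** The point holds in a limited form. The Protocol fixes a denominator that includes men already diagnosed with HIV, and its eligibility criteria let them in. If none of them reports a test, the rate and the absolute difference shrink by (1−p). Over assumed shares of 3% to 15%, an illustrative 8.0-point difference becomes 7.8 to 6.8 points. Compared with excluding diagnosed men, the power cost is about 0.01 at p = 3% (0.772 v 0.766) and 0.03 at p = 15% (0.717 v 0.684).

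This is attenuation, not bias towards either video. The risk ratio is preserved when diagnosed men report no tests. The primary outcome and the sample size of 1170 are unaffected. The conclusion that some misclassification occurs needs only that some participants are already diagnosed; its size rests on p, r and t, none of which the Protocol gives. The main gain from a change is an uptake rate that can be interpreted; the gain in power is minor. It is an optional improvement to one secondary outcome.

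**What to change.** In Appendix 2, define the HIV-testing denominator as participants who followed up and reported no HIV diagnosis at baseline, and count tests in the numerator among those same participants. Check that the survey given immediately before the video asks about prior HIV diagnosis, and add the item if it does not. The restriction rests on pre-intervention information, so it adds no post-randomisation selection beyond the follow-up condition already in the definition. Keep the all-followed-up version as a sensitivity analysis. Leave the STI-testing denominator unchanged, since a prior HIV diagnosis does not remove the reason to test for other infections.

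The cost is one line in Appendix 2 and at most one survey item. The item is sensitive and some diagnosed men will not disclose, so part of the dilution will remain. The denominator also becomes slightly smaller: at p = 10%, 526 × 0.9 = 473 per arm.
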